11.1 TOXICITIES/SIDE EFFECTS

The toxicities associated with radiation therapy to the prostate can be classified as either early (occurring within 90 days of treatment) or late (after 90 days). For the purpose of this study, the CTCAE v4.0 will be used as the primary endpoint to assess treatment-related toxicity. We expect that based on our prior studies^{14, 15}, 20% of patients of patients with have grade 2 or higher GU toxicity. The treatment will be considered to have significantly higher toxicity if ≥40% of patients in this study have ≥grade 2 at 12 months.

DEFINITIONS:

1. Adverse Event (AE)
 - a. An AE is defined by the GCP (Guide to Good Clinical Practice) as any undesirable experience occurring to a subject during a clinical trial, whether or not it is considered related to the investigational product(s).
2. Serious Adverse Event (SAE)
 - a. An SAE is an adverse experience that:
 - i. Is fatal or life-threatening
 - ii. Is disabling
 - iii. Results in hospitalization or prolongation of hospitalization
 - iv. Results in a congenital anomaly or occurrence of malignancy
 - v. Any urinary or rectal toxicity that is grade 3 or higher
3. Unexpected Adverse Event (UAE)
 - a. A UAE is an experience not previously reported (in nature, severity, or incidence) in the current Investigator's Brochure or general investigational plan.

Toxicities associated with radiation treatment include increased urinary frequency, urgency, weak stream, and nocturia. Other toxicities that may be related to radiation are fatigue, dysuria, hematuria, erectile dysfunction, urinary obstruction (due to edema or stricture), proctitis, bowel

injury or secondary cancers. Urinary, rectal, and erectile toxicities will be measured using IPSS, CTCAE v 4.0, and EPIC validated instruments (appendix).

The probability of severe (grade 3 or higher) urinary or rectal toxicity is expected to be $\leq 5\%$ which is currently observed rate of severe toxicity reported using standard combined brachytherapy and conventionally fractionated external beam radiation at MSKCC.¹⁴

To insure that unexpected significant toxicity is identified as early as possible with this treatment, we will observe the first 6 patients for a minimum of 3 months before enrolling any additional patients. If more than one patient has a grade 3 toxicity, we will wait 12 months before resuming accrual. If 4 or more patients of the first 6 patients have grade 3 or higher toxicity at 3 months we will terminate the study.

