12.1 CRITERIA FOR THERAPEUTIC RESPONSE/OUTCOME ASSESSMENT

The primary objective of this study is to assess toxicity associated with combined LDR brachytherapy and hypofractionated radiation therapy for intermediate risk prostate cancer at 12 months via CTCAE v4.0. Both acute and late toxicity associated with radiation therapy will be evaluated in a fashion similar to those used in prior studies of radiation therapy in prostate cancer patients. All grade 2 or higher toxicities will be evaluated and attributed to radiation therapy or not. Evaluation will be carried out prior to treatment to serve as a baseline. During each subsequent followup visit, patients will be asked to complete questionnaires (IPSS, IIEF, and EPIC) and asked about symptoms. The primary expected toxicities are genitourinary and gastrointestinal (rectal). Sexual function assessment is included but is not considered an SAE.

The following instruments will be used in the evaluation of toxicities:

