14.0 BIOSTATISTICS

The primary objective is to assess the toxicity of hypofractionated radiation therapy in combination with brachytherapy for the treatment of intermediate risk prostate cancer. To set up a decision rule we will focus on the CTCAE v 4.0 (see appendix) grade 2 or higher GU toxicity observed at the 1-year follow-up time (+/- 4 weeks). We will enroll 40 evaluable patients, and if 12 or more patients have a CTCAE v4.0 grade 2 or higher toxicity at 1 year, this treatment will be deemed too toxic and the study will be stopped. Otherwise it will be declared safe. This decision rule has the following probabilities of declaring treatment unsafe

True toxicity rate	0.15	0.20	0.25	0.30	0.35	0.40	0.45
Probability of declaring unsafe	1%	8%	28%	56%	79%	92.9%	98.2%

Patients who withdraw, die due to reasons other than toxicity, or fail to provide the 1-year CTCAE v4.0 GU toxicity status will be replaced by new patients. To this end we may need to enroll an additional 4 patients (10%).

For the secondary objectives, all toxicities will be tabulated by type and grade. Post-treatment PSA values will be summarized numerically and graphically. Time to PSA relapse will be analyzed by Kaplan-Meier estimation. The pathologic response rates at 24-36 months will be calculated as sample proportion based on the available patients and confidence intervals will be provided. Erectile function evaluated by IIEF will be summarized by descriptive statistics.

It is expected that it will take approximately 3 years to accrue the total of 45 patients.

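### Section 14's verdict of 'safe' has no grade 3 or higher criterion, so it can be reached even when the observed severe-toxicity rate excludes the protocol's own 5% expectation

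*Combined protocol and SAP*

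**What the plan says.** Section 14.0 bases its decision on "grade 2 or higher GU toxicity observed at the 1-year follow-up time (+/- 4 weeks". The cut-off reads: "We will enroll 40 evaluable patients, and if 12 or more patients have a CTCAE v4.0 grade 2 or higher toxicity at 1 year". The consequence of reaching that number, and the alternative if it is not reached, are given as: "this treatment will be deemed too toxic and the study will be stopped. Otherwise it will be declared safe". The cut-off sentence does not repeat the word GU, but the sentence before it and the replacement rule after the table both specify GU status, so I read the count as GU only. Section 14.0 otherwise tabulates toxicities by type and grade, with no threshold.

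Section 11.1 gives two expectations. For the counted endpoint it is "20% of patients of patients with have grade 2 or higher GU toxicity". For severe events: "The probability of severe (grade 3 or higher) urinary or rectal toxicity is expected to be" at most 5%, with no time point. Section 12.1 frames the aim broadly: "The primary objective of this study is to assess toxicity associated with combined LDR brachytherapy and hypofractionated radiation therapy".

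Grade 3 events are used in two other places, both in section 11.1:

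- **First six patients.** They are watched for at least 3 months before further enrolment. More than one patient with grade 3 toxicity leads to a 12-month wait. The termination rule is: "If 4 or more patients of the first 6 patients have grade 3 or higher toxicity at 3 months we will terminate the study".
- **SAE review.** Any grade 3 or higher urinary or rectal toxicity is an SAE. The principal investigator and investigators review SAEs and may continue, modify or discontinue, by criteria said to be in section 14.0.

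**The concern.** The verdict word is broader than the quantity behind it. The count does not distinguish 11 patients with grade 2 toxicity from 11 with grade 3 or 4, and it is blind to severe rectal toxicity. The 5% figure in section 11.1 is the protocol's only benchmark for severe toxicity, and no criterion for the conclusion uses it. The trial's stated purpose (section 3.0) is to establish the toxicity of a combination described as not yet studied. A report of 'safe' alongside a severe-event rate that statistically excludes the protocol's own expectation would mislead, even though the rule had been followed exactly.

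**Working it through.** **Inputs.** n = 40 and cut-off 12 (section 14.0). Expected grade 2 or higher GU rate 20% and severe rate at most 5% (section 11.1). Historical late GU toxicity: 21% grade 2 and 3.1% grade 3 or higher (section 3.0).

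**1. The plan's own table.** The table is introduced by "This decision rule has the following probabilities of declaring treatment unsafe". With X ~ Binomial(40, p), P(X ≥ 12) at p = 0.15, 0.20, 0.25, 0.30, 0.35, 0.40, 0.45 is 1.2%, 8.75%, 28.5%, 55.9%, 79.5%, 92.9%, 98.2%. The stated values are 1%, 8%, 28%, 56%, 79%, 92.9%, 98.2%. The table is reproduced to within a percentage point, so the rule is understood correctly.

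**2. Observed data that are called safe.** Exact (Clopper-Pearson) 95% intervals for the grade 3 or higher rate:

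| Grade 3+ of 40 | Rate | 95% CI |
|---|---|---|
| 5 | 12.5% | 4.2% to 26.8% |
| 6 | 15% | 5.7% to 29.8% |
| 11 | 27.5% | 14.6% to 43.9% |

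From 6 upward the interval excludes 5%. Any GU count from 6 to 11 is compatible with a total of 11 or fewer, and so with 'safe'. Grade 3 or higher rectal events have no ceiling in the rule. If the true grade 2 or higher GU rate is 20%, the verdict is 'safe' with probability 1 − 0.0875 = 91%, whatever the rectal rate.

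**3. Probability of 'safe' at a raised severe rate.** Three and four times 5% are 15% and 20%. The rule responds only to the total T = (grade 2 only) + (grade 3 or higher), so P(safe) = P(Binomial(40, T) ≤ 11).

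| Assumption | T at 15% / 20% severe | P(safe) |
|---|---|---|
| Total stays at 20% | 20% / 20% | 91% / 91% |
| Total stays at 25% | 25% / 25% | 72% / 72% |
| Grade 2 alone stays at 15% (20% − 5%) | 30% / 35% | 44% / 21% |
| Grade 2 alone stays at 21% (historical) | 36% / 41% | 17% / 5.5% |

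P(safe) exceeds 50% only when T is below about 28.9%.

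**4. The first-six rules.** Assume the same 15% or 20% rate applies by 3 months. The pause has probability P(Binomial(6, p) ≥ 2) = 22% or 34%. Termination has probability P(Binomial(6, p) ≥ 4) = 0.6% or 1.7%.

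**5. An illustrative grade 3 or higher bound.** P(Binomial(40, p) ≥ 5) is 4.8%, 37%, 74% and 92% at p = 5%, 10%, 15% and 20%. Requiring both a total of 11 or fewer and fewer than 5 severe events gives

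P(safe) = Σ (k = 0 to 4) P(Binomial(40, g3) = k) × P(Binomial(40 − k, g2/(1 − g3)) ≤ 11 − k).

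- Expected case (g3 = 5%, g2 = 15%): from 91.2% to 88.2%.
- g3 = 15%, g2 = 10%: from 71.5% to 25.4%.
- g3 = 15%, g2 = 15%: from 44% to 20%.
- g3 = 20%, g2 = 15%: from 21% to 5%.

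Here every severe event is a GU event inside the total.

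**The case against.** A reader might infer that a regimen with three to four times the expected severe rate would usually be declared safe. The documents do not support that. It requires extra severe events to replace grade 2 events, so that the total stays at 20% to 25%; a 20% severe rate within a 20% total leaves no grade 2 at all. Historically grade 2 outnumbered grade 3 or higher by about 7 to 1 (21% against 3.1%). If severe events add to a grade 2 background of 15% to 21%, the existing rule calls the regimen unsafe in 56% to 95% of trials. This objection stands, and it limits any statement of frequency.

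The benchmark is also not matched to the endpoint. The 5% covers urinary or rectal toxicity with no time point, whereas the rule covers GU at 1 year. Three to four times the historical late GU rate would be 9.3% to 12.4%. This too stands, as a stated assumption.

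Nor is severe toxicity unwatched. The pause rule has a real chance of triggering, its 12-month wait runs past the 90-day early period, every grade 3 or higher urinary or rectal event is reviewed, section 16.3 describes committee oversight, and counts by grade will be tabulated. These are genuine safeguards during conduct. None of them enters the final verdict, however, and the SAE review refers to section 14.0 for criteria that contain no grade 3 or higher limit.

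**Conclusion.** The point holds as a defect in what the trial may conclude. Section 14.0 can yield an unqualified 'safe' with 6 to 11 of 40 patients at grade 3 or higher GU toxicity, each count excluding 5%, and with any number of severe rectal events. That follows from the rule itself and needs no assumption about the mix of grades, beyond reading the count as GU only.

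The probability of such a verdict does depend on the mix. At a true severe GU rate of 15% to 20% it ranges from 91% (total fixed at 20%) to 5.5% (20% severe added to 21% grade 2). These figures assume that the 5% urinary-or-rectal benchmark may be applied to 1-year GU status. The documents do not say which mix to expect, so the range should be quoted, not one end of it.

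**What to change.** **Label.** In section 14.0, replace the sentence that declares the treatment safe with: *Otherwise grade 2 or higher urinary toxicity at 1 year will be declared acceptable.*

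**Reporting.** Add that the proportion with grade 3 or higher urinary or rectal toxicity, over a stated time window, will be reported with an exact 95% interval against section 11.1's 5%, and that an unqualified claim of safety will not be made if that interval lies above 5%.

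**Cross-reference.** Reconcile the SAE evaluation text in section 11.1 with section 14.0, so that it is clear which criteria the review uses.

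**Optional.** If the sponsor prefers a formal grade 3 or higher bound for the conclusion, section 14.0 should state its window, say what failing it means for the verdict, and print its operating characteristics beside the existing table. Five or more of 40 is an illustration only; other bounds are defensible.

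**Cost.** The label and reporting changes take a few sentences and use data already collected; the price is a narrower claim. With the illustrative bound, P(not declared safe) in the expected case rises from about 9% to 12% if all severe events are GU events within the 20%. It rises by more if rectal or acute events count. For example, the historical acute and late GU rates sum to 2.3% + 3.1% = 5.4% if they fall in different patients. P(5 or more of 40) is 6% at 5.4%, and 15% and 21% at assumed rates of 7% and 8%. These changes concern the trial's conclusion, not the management of patients.

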1.0 PROTOCOL SUMMARY AND/OR SCHEMA

ASSESSd

- Eligibility
 - Organ-confined prostate cancer
 - Intermediate risk patients
 - PSA 10-20 ng/ml, or Gleason score = 7 or clinical stage T2b/T2c
- Obtain Informed Consent
- Register Patient

INTERVENTION

- Prostate brachytherapy low dose rate (Pd-103)

THEN after 4 weeks

- Hypofractionated image-guided external beam radiation therapy to prostate and seminal vesicles - (25 Gy in 5 fractions)

POST TREATMENT EVALUATIONS (months 1, 3, 6, then every 6 months for 36 months)

- International Prostate Symptom Score (IPSS)
- International Index of Erectile Function (IIEF)
- Toxicity based on NCI CTCAE (v4.0)
- EPIC
- DRE
- PSA
- Prostate biopsy once at 24-36 months

This study will enroll participants with localized, intermediate risk prostate cancer (T2b/c or Gleason 7 or PSA 10-20 ng/mL). Patients enrolled in the study will undergo low dose rate (LDR) prostate brachytherapy using Pd-103 followed approximately 4 weeks later with hypofractionated image-guided external beam radiation therapy (25Gy in 5 fractions; 5Gy x 5 fractions every other day) to the prostate and seminal vesicles. Both brachytherapy as well as external beam will be performed according to our current standards of practice using the same equipment, techniques, and treatment planning procedures.

Patients will be followed post-treatment at 1, 3, 6 (+/- 4 weeks) and every 6 months (+/- 4 weeks) thereafter until 36 months. During the post-treatment followup, patients will be evaluated for urinary, bowel/rectal and sexual toxicity. Toxicity will be assessed according to CTCAE v4.0, IPSS, IIEF and EPIC validated instruments. Baseline measures of these domains will be obtained prior to treatment at the time of enrollment. Serum PSA levels will be drawn on the same schedule as clinical followup. Post-treatment prostate biopsies will be obtained once between 24-36 months post-treatment to evaluate pathologic response to therapy.

The total number of participants enrolled will be 45 to be accrued in approximately 3 years.

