10.1 EVALUATION DURING TREATMENT/INTERVENTION

Patients who cannot meet the necessary dosimetric constraints will not be eligible for participation in the study and will be withdrawn from study, since they will already be enrolled at this time

- There will be at least one status check visit during the course of hypofractionated external beam radiotherapy.
- Participants will have clinic follow-up visits at 1, 3, and 6 months (+/- 4wks) posttreatment.
- Then at 6 month intervals (+/- 4wks) post treatment.
- Follow-up scheduling is based on the last day of hypofractionated treatment.
- At each followup visit, patients will undergo standard DRE and serum PSA. Patients will also be asked to complete sexual quality of life questionnaires (EPIC), and urinary and rectal quality of life questionnaires (IPSS and IIEF), which will be captured per standard of care and be assessed for toxicity using CTCAE 4.0. If patient is unable to come in for a followup appointment, a telephone followup will suffice and the PSA and DRE will be deferred. IPSS, IIEF, and EPIC questionnaires can be completed over the phone or sent to patients via mail, fax, or electronic mail by the physician or the physician's office assistant if the patient is unable to come in for a follow-up appointment. If the patient cannot be reached by phone or prefer to complete the questionnaires personally, the questionnaires will be sent via mail, fax or electronic mail. The questionnaires sent directly to patients must be blank forms with no patient identifiers, only study ID numbers. If questionnaires are sent via mail, the patient must be provided with a pre-filled business envelop that will allow patients to return it with no expense. Patients must also have the option of returning questionnaires by electronic mail or fax. If a patient is unable to come in for a follow-up appointment or complete the questionnaires over the phone, the method by which questionnaires are sent to patients and the method by which questionnaires are returned will be determined based on the patient's preference or if they are unable to be contacted by phone, the contact information on file for the patient as some patients may not have access to a phone, fax or electronic mail. A repeat prostate biopsy will be completed between months 24 and 36 for pathologic response assessment. This is a standard assessment tool.

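### Does the gap between 40 + 4 = 44 patients and the stated total of 45 undermine the 12-event toxicity rule?

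*Combined protocol and SAP*

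**What the plan says.** Section 14.0 sets the decision rule: "We will enroll 40 evaluable patients, and if 12 or more patients have" a grade 2 or higher toxicity at 1 year, the treatment is judged too toxic. A row of probabilities of declaring the treatment unsafe follows, for true rates from 0.15 to 0.45.

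On losses, the same section says that patients who withdraw, die of causes other than toxicity, or "fail to provide the 1-year CTCAE v4.0 GU toxicity status will be replaced by new patients". It then adds "To this end we may need to enroll an additional 4 patients (10", where the bracket gives the percentage.

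The total appears twice. Section 1.0 says "The total number of participants enrolled will be 45 to be accrued in approximately 3 years", and Section 14.0 closes with "It is expected that it will take approximately 3 years to accrue the total of 45 patients".

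Two other statements bear on timing. Section 10.1 says "Follow-up scheduling is based on the last day of hypofractionated treatment", so the 1-year assessment is dated from the end of external beam treatment. Section 11.1 says "we will observe the first 6 patients for a minimum of 3 months before enrolling any additional patients".

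**The concern.** The planned size of a trial should be one number, and here the parts add to 44 while the stated total is 45. No sentence explains the extra patient.

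The larger worry lies behind the slip. A fixed threshold of 12 events has the printed error rates only if exactly 40 patients are counted. One-year status comes late, so some replacements may have to enter before it is known how many are needed, and the evaluable number could pass 40. It could also fall short of 40 if 45 were treated as a ceiling. The plan does not say whether the first 40 or all evaluable patients are then compared with 12. In principle that choice could be made after the results are known, and it decides the primary verdict. With all 45 evaluable and the threshold left at 12, the chance of a false alarm at a true rate of 0.20 would be 17.4%, about twice the intended figure.

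**Working it through.** **Inputs from the documents.** 40 evaluable patients, threshold 12, 4 extra patients (10%), total 45 and the printed probability row (all Section 14.0); total 45 again (Section 1.0); 20% expected and 40% unacceptable toxicity (Section 11.1).

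**Step 1. Enrolment arithmetic.**
- Adding 10% of the evaluable number: 40 × 1.10 = 44.
- Allowing for 10% loss among those enrolled: 40 / 0.90 = 44.4, rounded up to 45.
- Expected evaluable: 44 × 0.90 = 39.6; 45 × 0.90 = 40.5.

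Both figures follow from a 10% allowance, applied to different bases. That this is how 45 arose is an inference. On that allowance, 45 is the number that yields 40 on average.

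**Step 2. Reproduce the printed row.** P(unsafe) = P(X ≥ 12), X ~ Binomial(n, p).

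| True rate | Printed | n = 40 | n = 44 | n = 45 |
|---|---|---|---|---|
| 0.15 | 1% | 1.2% | 2.6% | 3.0% |
| 0.20 | 8% | 8.75% | 15.4% | 17.4% |
| 0.25 | 28% | 28.5% | 42.0% | 45.4% |
| 0.30 | 56% | 55.9% | 70.6% | 73.8% |
| 0.35 | 79% | 79.5% | 89.3% | 91.0% |
| 0.40 | 92.9% | 92.9% | 97.2% | 97.8% |
| 0.45 | 98.2% | 98.2% | 99.5% | 99.6% |

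The row reproduces at n = 40, with 8.75% apparently cut to 8%. It does not reproduce at 44 or 45. The rule was built for 40, whichever total is right.

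**Step 3. Count everyone evaluable.** Assume 45 enrolled, independent losses at the plan's 10%, no replacement beyond 45, and all evaluable patients compared with 12. An enrolled patient is then a counted event with probability 0.9p, so P(unsafe) = P(Binomial(45, 0.9p) ≥ 12).

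| True rate | n = 40 | 45 enrolled, 10% loss, all counted |
|---|---|---|
| 0.15 | 1.2% | 1.4% |
| 0.20 | 8.75% | 9.7% |
| 0.25 | 28.5% | 30.3% |
| 0.30 | 55.9% | 57.7% |
| 0.35 | 79.5% | 80.3% |
| 0.40 | 92.9% | 93.1% |
| 0.45 | 98.2% | 98.2% |

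The largest shift is 1.8 points, at 0.25.

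**Step 4. How often the choice of set matters.** The first 40 are a subset of all evaluable patients, so the two verdicts can differ only when more than 40 are evaluable. The probability is the sum over n = 41 to 45 of P(Binomial(45, 0.9) = n) × [P(X ≥ 12 | n) − P(X ≥ 12 | 40)]. It comes to 1.7% at 0.20, 4.1% at 0.30 and 1.3% at 0.40.

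**Step 5. Range for loss rates the documents do not give.**
- Assumed 5% loss: 13.3% at 0.20 and 96.0% at 0.40, with verdicts differing in 4.5% of trials at 0.20 and 10.4% at 0.30.
- Assumed 15% loss: 6.9% at 0.20 and 88.6% at 0.40.
- All 45 evaluable, the case behind the 17.4%: 0.9^45 = 0.9% chance at 10% loss.

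**Step 6. Timing.** Assume even accrual outside a 3-month pause after the sixth patient: 45 / (36 − 3) = 1.36 patients a month. The 40th enters at 40 / 1.36 + 3, about month 32. One-year status comes about 13 months after implant (about 4 weeks to external beam, then 12 months), so about 22 of the first 40 have it by then and about 18 do not.

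**The case for a change.** The strongest argument for a change is prespecification. Replacement aims at 40, but the timing in Step 6 makes an exact landing unlikely. Under the Step 3 assumptions the evaluable number is above 40 in 53% of trials, exactly 40 in 18% and below 40 in 29%. The verdict is the primary result, and a sentence naming the counted set would cost almost nothing. With losses lighter than planned, the choice matters more (10.4% of trials at 5% loss and a true rate of 0.30).

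Part of this stands. The plan has no tie-break for surplus patients, and the two totals do not agree. The rest is weaker than it looks:

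- The 29% needs 45 to be a hard ceiling. The plan states none and says without limit that patients lacking 1-year status are replaced.
- Eighteen patients without a 1-year result are not eighteen unknown replacement needs. Withdrawals for unmet dosimetric constraints (Sections 10.1 and 13.1) arise around external beam planning, and other withdrawals and deaths are known when they occur. Only a missed 1-year assessment is learned late, and Section 10.1 allows telephone follow-up.
- The 5% loss figures assume that all 45 are enrolled regardless of need. The text says extra patients may be needed; with few losses, few replacements are called for.
- Counting more than 40 against 12 raises both false alarms and detection. In a toxicity study that errs towards caution.
- The obvious repairs have costs. Writing 5 extra patients clashes with the printed 10%, since 5/40 = 12.5%. Restricting the count to the first 40 leaves some treated patients out of the formal decision. A threshold for each evaluable number needs a table.

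**Conclusion.** No change to the plan follows. The one-patient gap is a clerical slip between two ways of applying a 10% allowance. Reconciling it alters neither the rule, its error rates nor the planned total.

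The counting question is missing detail with an evident reading. Section 14.0 ties the threshold to 40 evaluable patients, the probability row confirms that number, and the replacement sentence serves to reach it. An analyst faced with a few surplus patients would apply the rule to the first 40 by registration and report all evaluable patients beside it.

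Even on the other reading, at the plan's own 10% loss, the false-alarm rate at 0.20 rises by about 1 point (8.75% to 9.7%) and detection at 0.40 by about 0.2 points (92.9% to 93.1%). The verdict depends on the choice in roughly 1% to 4% of trials at 0.20, 0.30 and 0.40. These figures assume 45 enrolled, independent losses and no replacement beyond 45. Lighter losses with all 45 still enrolled would enlarge them as in Step 5, towards caution.
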